### 2.2 Study Endpoints

#### 2.2.1 Efficacy

**Primary efficacy endpoint:**

- The proportion of responders in each treatment group achieving seizure activity cessation within 2 minutes after the administration of the study drug and no recurrence of seizure activity within 2 hours

**Secondary endpoints:**

- Seizure episode severity assessed by subject and/or Staff Caregiver
- Use of rescue medication

- Secondary generalization (evolution to a complex partial seizure and/or a generalized tonic-clonic seizure)

#### **Exploratory endpoints:**

- Number of seizures during the 4, 6, and 12 hour time periods after study drug administration
- Time to next seizure event with start time >2 minutes after study drug administration

#### **2.2.2 Pharmacokinetic**

Blood samples will be collected for plasma alprazolam concentration measurement pre-dose and then at 10, 30, and 60 minutes, and 2 and 6 hours after the dosing of the study drug.

#### **2.2.3 Safety**

Safety and tolerability will be assessed by evaluating adverse events (AEs), vital signs, concomitant medications, clinical laboratory, and electrocardiogram (ECG) results, as well as neurological and physical examinations. Sedation will also be assessed using a subject visual analog scale (VAS).

### **2.3 Sample Size**

There are no studies in the literature to provide reliable estimates of active treatment or placebo response rates for this study. Assuming a 10% drop-out/protocol violation rate, approximately 115 subjects will be enrolled in the double-blind part of the study to provide approximately 35 evaluable subjects per treatment arm. Enrollment may be stopped after 105 evaluable subjects have completed the study.

Approximately 30% of the overall study population randomized in the study may be subjects being treated with chronic daily benzodiazepines as part of their epilepsy management. Since the effect of concomitant chronic daily benzodiazepines use on study treatment is unknown, a 50% response rate for chronic benzodiazepines users on active treatment arms is assumed. For subjects who are not chronic benzodiazepines users, a response rate of 60% for active treatment arms is assumed. With up to 30% of study population being chronic benzodiazepines users and these response assumptions, a 57% response for the active treatment arm is targeted.

Power calculations assume a 2-sided test and significance level of 0.05 with 90% power and are based on the assumption that the proportion of responders with STAP-001 is 57% (best active treatment arm) whereas the assumed placebo responder rate is 20%.

## **3. STATISTICAL METHODS**

### **3.1 General**

All data will be analyzed using the Statistical Analysis System (SAS®; Version 9.4).

Safety and efficacy data will be summarized and presented by treatment group and time point in summary tables. Continuous variables will be presented by descriptive statistics: n, mean, standard deviation (SD), median, minimum, and maximum. Categorical variables will be tabulated by frequency count and percentage.

When the actual treatment received by a subject is different from the randomized treatment assigned, the subject will be analyzed per the randomized treatment for the efficacy parameters (using the ITT, and mITT populations); while the subject will be analyzed per actual treatment that was taken for the safety parameters (using the safety population).

Unless otherwise stated, all statistical tests will be 2-sided hypothesis tests performed at the 5% level of significance for main effects and all confidence intervals (CIs) will be 2-sided 95% confidence intervals.

For the Treatment Period, data will be summarized by active treatment by dose level versus placebo-treated subjects (i.e., by treatment group). All data for analysis will be listed by subject.

### 3.2 Subject Disposition, Demographics, Baseline Characters and Study Drug Compliance

- Disposition will be summarized by randomized treatment group. The number and percentage of subjects, who are randomized, treated, prematurely discontinued, and complete the study will be summarized.
- Baseline characteristics will be summarized by treatment group.
- The number of subjects in each cohort's treatment group will be summarized for each investigative site for the Treatment Period.
- Medical history will be listed with reported terms.
- Concomitant medications will be summarized by World Health Organization Drug Dictionary Anatomical-Therapeutic-Chemical (WHODRUG\_ATC) classification and preferred term.

### 3.3 Analysis of Study Endpoints

#### 3.3.1 Efficacy

All statistical tests will be 2-sided with a significance level of 0.05. Testing will be performed only for the Treatment Period.

Data will be summarized by active treatment by dose level versus placebo-treated subjects (i.e., by treatment group). Continuous measures will be summarized descriptively (mean, standard deviation, median, minimum value, and maximum value) and categorical measures will be presented as number and percentage.

The primary efficacy analysis will be conducted following completion of the Treatment Period for the last subject and data base lock.

#### Primary Efficacy Endpoint

The primary efficacy endpoint will be the proportion of responders in each treatment group achieving seizure activity cessation within 2 minutes after the administration of the study drug and no recurrence of seizure activity within 2 hours. The primary endpoint will be analyzed with a chi-squared test. The overall treatment comparison, as well as pair-wise comparisons between each dose level and placebo will be performed. The estimates of the treatment difference versus placebo and their 95% confidence interval will be presented.

There will be no adjustment for multiple treatment group comparisons in this dose-ranging Phase 2b study. The dose-response relationship will be explored with a regression analysis.

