7.2. Method of Treatment Assignment and Blinding (Double Blind Phase)

After admission to the in-patient unit subjects will be randomly assigned (1:1:1) to one of 2 doses of STAP-001 (1 mg or 2 mg) or *Staccato* placebo. Randomization will be stratified by the use of inducing vs non-inducing AEDs, and by use of daily benzodiazepines (yes or no) to ensure even distribution of treatment assignments in the two cohorts.

All study participants will be blinded to study drug assignment. The device and packaging of STAP-001 and placebo will be identical in appearance.

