7.3. Rationale for Study Design

Part 1 is open-label and designed to assess feasibility of the study. Part 2 is double blind and randomized and is designed to assess treatment efficacy and safety. Double-blind, randomized, placebo-controlled studies are considered optimal for obtaining unbiased estimates of the efficacy and safety of investigational products. The single dose administration of STAP-001 during a seizure episode is sufficient to evaluate the safety and potential of the product as an acute treatment of an epileptic episode.

A large proportion of subjects with epilepsy with a predictable seizure pattern are taking chronic daily benzodiazepine medication. It has been speculated that the efficacy of STAP-001 may be reduced in these subjects because of potential cross-tolerance between benzodiazepines. However, it is deemed important to evaluate the efficacy of STAP-001 in this population. It is also important to evaluate the tolerability and safety of STAP-001 in subjects on chronic benzodiazepine treatment in a controlled environment. Therefore, approximately 30% of the overall study population randomized in the study may be subjects being treated with chronic daily benzodiazepines as part of their epilepsy management. The subjects will be stratified by concomitant chronic daily benzodiazepine use to ensure even distribution of benzodiazepine use across treatment arms.

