#### 1.2.2 Part 2: Double-Blind

After admission to the in-patient unit eligible and qualified subjects will be stratified by the use of inducing vs non-inducing AED and the use of chronic daily benzodiazepines (yes or no) and randomly assigned (1:1:1) to one of two doses of STAP-001 (1 mg or 2 mg) or Staccato placebo. A blood sample for PK analysis (pre-dose) will be obtained. For each subject, a single seizure episode will be treated and assessed. Study medication will be self-administered (when feasible) or administered by a Staff Caregiver when a predictable seizure episode starts. Assessment of the seizure activity is based on clinical observation by the Staff Caregiver using a stop watch. In addition, a video EEG will record the occurrence, start time, and duration, of the seizure event. PK samples will be collected 10, 30 and 60

minutes, and 2 and 6 hours after the administration of the study drug. If possible, subjects will signal when they experience a seizure event. Subject will be under video EEG surveillance throughout the Treatment Phase. The Staff Caregiver will signal the event for the video EEG recording, starts the stop watch at the time of drug administration, and mark the occurrence of the seizure event on a seizure diary. If the seizure episode does not stop within 5 minutes of the study drug administration, rescue medication other than alprazolam may be administered at the discretion of the principal investigator per the protocol of the research unit. The study exit procedures will be conducted 24 to 32 hours after the administration of study medication or when the subject discontinues from the study.

After discharge from the in-patient unit there will be a safety-follow-up phone contact  $14 \pm 2$  days after the subject received the study medication.

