## 2. ELABORATION OF STUDY PROTOCOL

### 2.1 Study Populations

Five analysis populations will be defined and analyzed:

1. The Efficacy Population (ITT population) will include all subjects who have a seizure event and receive study drug during the Treatment Period.
2. Modified Intent to Treat (mITT) population will consist of all subjects who have a seizure event, receive study drug, and have had at least one evaluation after study drug administration. mITT will be used for primary efficacy analysis.
3. The Per Protocol Population will include all subjects in the Efficacy Population who were dosed according to protocol and have no major protocol deviations. Major protocol deviations will be identified by Engage Therapeutics, Inc., before the database is locked and unblinded.
4. The PK Population will include all subjects who receive study drug and have at least one pharmacokinetic data point during the Treatment Period. Subjects who receive placebo will be excluded from the PK Population. PK concentrations will be analyzed using PK population.
5. The Safety Population will include all subjects who receive study drug during the Treatment Period from both Part 1 Open-label Feasibility and Part 2 Double-blind. All safety parameters will be analyzed using safety population.

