#### 4.1.2 Summary of Efficacy Endpoints

Table 14.2.1.1 Result of Treatment Response – mITT Population

Table 14.2.1.2 Result of Treatment Response – PP Population

Table 14.2.2.1 Results of Seizure Episode Severity Scale – mITT Population

Table 14.2.2.2 Results of Seizure Episode Severity Scale – PP Population

Table 14.2.3.1 Result of Use of Rescue Medication – mITT Population

Table 14.2.3.2 Result of Use of Rescue Medication – PP Population

Table 14.2.4.1 Result of Secondary Generalization Evolution – mITT Population

Table 14.2.4.2 Result of Secondary Generalization Evolution – PP Population

Table 14.2.5.1 Summary of Seizure Number after Study Drug Administration – mITT Population

Table 14.2.5.2 Summary of Seizure Number after Study Drug Administration – PP Population

Table 14.2.5.3 Treatment Comparison of Seizure Number after Study Drug Administration – mITT Population

Table 14.2.5.4 Treatment Comparison of Seizure Number after Study Drug Administration – PP Population

Table 14.2.6.1 Kaplan-Meier Analysis of Time to Next Seizure Event after Study Drug Administration – mITT Population

Table 14.2.6.2 Kaplan-Meier Analysis of Time to Next Seizure Event after Study Drug Administration – PP Population

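### The primary chi-squared test leaves out both randomisation strata, its confidence interval has no named method, and no listed table title shows response by benzodiazepine use: a low-cost refinement to a valid analysis

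*SAP*

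**What the plan says.** SAP 1.2.2 has Part 2 subjects "stratified by the use of inducing vs non-inducing AED and the use of chronic daily benzodiazepines (yes or no") and allocated 1:1:1. Two binary factors give four strata. Protocol 7.2 gives the purpose as "to ensure even distribution of treatment assignments in the two cohorts".

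For the primary endpoint, SAP 3.3.1 states: "The primary endpoint will be analyzed with a chi-squared test". This covers the overall comparison and each dose against placebo. Protocol 13.4.2 has the same wording. Neither document names a stratum or covariate for this test. On precision, the SAP says only "The estimates of the treatment difference versus placebo and their 95% confidence interval will be presented". A CMH test is named for the seizure severity scale, also without strata.

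On benzodiazepine users, Protocol 7.3 records a speculation that "the efficacy of STAP-001 may be reduced in these subjects because of potential cross-tolerance between benzodiazepines", then says "it is deemed important to evaluate the efficacy of STAP-001 in this population". The sample size sections (Protocol 13.1, SAP 2.3) assume 50% response in users and 60% in non-users on active treatment, with one placebo rate of 20%. In SAP 4.1.2 the responder tables are 14.2.1.1 and 14.2.1.2, each titled "Result of Treatment Response", for the mITT and per-protocol populations. No listed title is split by benzodiazepine use or AED type.

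**The concern.** An analysis normally reflects the way subjects were randomised. If the strata predict response in both arms, stratified randomisation removes between-stratum variation from the treatment difference, but the pooled chi-squared variance still includes it. The test then rejects too rarely under the null.

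Two further gaps do not depend on this. An interval method left open for the primary estimate can be chosen after the data are seen. And a question that the protocol calls important has no output among the listed table titles, so any later presentation by benzodiazepine use would look data-driven.

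**Working it through.** **1. The plan's own figure.** Inputs (SAP 2.3): 57% versus 20%, two-sided 0.05, 90% power.

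- Planning rate: 0.3 × 50% + 0.7 × 60% = 57%.
- Mean rate: (0.57 + 0.20)/2 = 0.385.
- n per arm = [1.960 × √(2 × 0.385 × 0.615) + 1.282 × √(0.57 × 0.43 + 0.20 × 0.80)]² / 0.37² = (1.349 + 0.816)² / 0.1369 ≈ 34.2, so 35.
- Exact power of the chi-squared test at 35 per arm is 90.7%. The plan's figure reproduces.

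**2. Power of a four-stratum CMH test.** Subjects are lost after randomisation, because the mITT population takes "all subjects who have a seizure event, receive study drug, and have had at least one evaluation after study drug administration". Balance within strata is therefore only approximate, and the simulations include a random 10% loss. The documents give no inducing-AED share, block size or response rate by AED type, so these are assumptions.

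At the plan's rates (active 60% in non-users and 50% in users, placebo 20% throughout), with 38 randomised per arm split 16/11/7/4 over the strata, power is 90.4% for chi-squared and 90.0% for CMH: -0.4 points. Inducing shares of 20-50% with 115 randomised in permuted blocks give -0.4 to -0.5.

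Next, suppose the strata are prognostic in both arms, with the overall rates held at 57% and 20%. Each odds ratio (OR) below is the factor by which the odds of response are lower in users, or in subjects on inducing AEDs:

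| OR (benzodiazepine, AED) | Inducing share | Power chi-squared → CMH | Change | Type I error, chi-squared / CMH |
|---|---|---|---|---|
| 1.5, 1 | 30% | 90.55 → 90.15 | -0.40 | 5.05 / 4.91 |
| 2, 2 | 30% | 90.77 → 91.00 | +0.23 | 4.81 / 4.90 |
| 3, 1 | 30% | 90.92 → 91.25 | +0.33 | 4.86 / 4.94 |
| 3, 3 | 30% | 91.25 → 92.37 | +1.12 | 4.54 / 4.89 |
| 4, 4 | 30% | 91.55 → 93.35 | +1.80 | 4.31 / 4.87 |
| 4, 4 | 50% | 91.75 → 93.80 | +2.05 | 4.11 / 4.92 |

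**3. Type I error.** With a flat 20% in every stratum and 10% loss, chi-squared has 5.1% and CMH 4.9%. With assumed rates of 35/16/3/1% in both arms (non-user/non-inducing, non-user/inducing, user/non-inducing, user/inducing), chi-squared has 3.9% and CMH 4.9%.

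A hand check of that case, with perfect balance at 15/10/6/4 per arm:

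- Mean rate: (15 × 0.35 + 10 × 0.16 + 6 × 0.03 + 4 × 0.01)/35 = 0.202.
- Total variance: 0.202 × 0.798 = 0.161.
- Within-stratum variance: (15 × 0.2275 + 10 × 0.1344 + 6 × 0.0291 + 4 × 0.0099)/35 = 0.142.
- The pooled test behaves as if its cut-off were 1.96/√(0.142/0.161) ≈ 2.09, a two-sided level of about 3.7%. Simulation gives 3.5% with perfect balance.

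**4. Collapsing strata.** A CMH test by benzodiazepine use alone has type I error of 4.5% in the 35/16/3/1% case. If only AED type matters (assumed 32% versus 4%), it has 3.8%, against 4.0% for chi-squared and 4.9% for four strata.

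**5. Interval method.** At 35 per arm, 57% versus 20%, exact coverage is 93.9% for Wald and 95.0% for Newcombe. In the simulations with loss, Mantel-Haenszel with the Sato variance covers 93.9-94.4% and Wald 94.1-95.5%, so the stratified interval is no better.

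**6. Benzodiazepine users.** 0.3 × 35 = 10.5, so about 10 per arm. At 50% versus 20%, the Wald half-width is 1.96 × √(0.25/10 + 0.16/10) = 39.7 points, and exact chi-squared power is 25.4%.

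**The case against.** The strongest reply is that nothing is wrong at the plan's own rates. The chi-squared test has 5.1% type I error there, CMH loses a little power, and the Protocol and SAP agree on a pre-specified test. Even distribution, the stated purpose of stratifying, is met whatever test is used. All of this stands, and it is why this is a suggestion and chi-squared may remain primary.

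Three limits also stand. The statement about tables rests on titles: SAP 4.1 and 6 refer to shells that were not available, and these could hold rows by benzodiazepine use or a named interval method. A rule that merges small strata into benzodiazepine use alone would lose the calibration gain when AED type drives response. And Protocol 7.3 does not promise a subgroup analysis; with about 10 users per arm a table can only describe.

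A reader might infer that leaving out the strata makes the primary test biased, invalid or underpowered. The documents do not support that. The test is unbiased and correctly sized, and it becomes conservative only when the strata predict response in both arms. The 50%/60% split does not show this: it applies to active arms only, placebo has a single rate, and no rate is given by AED type.

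**Conclusion.** The point holds as a cheap improvement. The document facts are clear: stratified randomisation, an unstratified primary test, no stated interval method, and no listed title showing response by benzodiazepine use.

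The gain is in calibration and is small. Four-stratum CMH stays near 4.9%, against 5.1% for chi-squared with flat strata and about 4% with strongly prognostic strata. Power is not the reason to change: about -0.4 points at the plan's rates, -0.4 to +0.4 for moderate prognostic effects, and about +2 at an odds ratio of 4 for both factors. These are results under assumed prognostic strengths, stratum sizes and random loss, and are not bounds.

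The case for naming an interval method and adding the descriptive table needs no simulation.

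**What to change.** Before unblinding:

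1. Analyse the primary endpoint with a CMH test stratified by the two factors as recorded at randomisation, overall (general association) and for each dose against placebo. Keep the unstratified chi-squared test as supportive, or reverse the roles if the sponsor prefers chi-squared as primary. Do not merge strata for small size; merge only when a stratum is empty or lacks one of the compared arms, and state in advance how.
2. Name a 95% interval method with near-nominal coverage, for example Newcombe. That interval is unstratified and could disagree with CMH in a borderline result, so state that the test governs.
3. Add one descriptive responder table by benzodiazepine use, with intervals and no claim. If the shells already contain it, cite it in SAP 4.1.2.
4. Record the departure from Protocol 13.4.2 in SAP 3.7, which now reports no change.

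The cost is SAP wording, one table and no new data. If CMH becomes primary, it also costs about 0.4 points of power at the plan's rates (about 1.1 in the extreme case of no balance between arms on the strata). As supportive output it costs no power.

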#### Secondary and Exploratory Efficacy Endpoints

Secondary and exploratory endpoints will be summarized by treatment group and if applicable, by assessment time point. Exploratory statistical testing may be performed if warranted. The Cochran-

Mantel-Haenszel (CMH) test for row-mean score difference will be used to test the treatment difference in the seizure episode severity. The Kruskal-Wallis test will be used to compare seizure frequencies. The time-to-next-seizure data will be summarized and displayed with Kaplan-Meier plots. No multiplicity adjustment will be implemented for exploratory tests.

### 3.3.2 Pharmacokinetics

The collection status of PK samples will be listed for each visit with scheduled pharmacokinetic sampling. Plasma concentrations of study drug and the active metabolites may be summarized separately, as appropriate.

PK parameters including maximum concentration ( $C_{max}$ ), time to maximum ( $T_{max}$ ), area under the concentration curve from 0 to the last measurable value ( $AUC_{last}$ ) will be estimated for each subject using non-compartmental methods. Since the time point range is 0 to 6 hours and the alprazolam half-life is 11 hours, we do not plan to estimate half-life or  $AUC_{inf}$ .

### 3.3.3 Safety Analysis

All safety summaries will be descriptive with no statistical hypothesis testing and based on the Safety Population. Subjects will be summarized according to the study drug received. (i.e., as treated), should it differ from the randomized treatment arm. All safety endpoints will be listed in by-subject data listings.

#### Adverse Events

An adverse event reported after informed consent and occurring before the first dose of study drug in the CRU/EMU will be considered a pre-treatment adverse event. Treatment-emergent adverse events (TEAEs) will be defined as any adverse event that occurs after administration of study drug.

- The number and percentage of subjects who experience TEAEs will be summarized by treatment group for the following:
  - By system organ class and preferred term
  - By severity, system organ class, and preferred term
  - By relationship to study drug, system organ class, and preferred term
  - Serious adverse events by system organ class and preferred term
  - TEAE by preferred term and overall frequency.
- Subjects who report the same preferred term on multiple occasions will be counted once for the preferred term: under the highest severity when summarized by severity and under the closest relationship to study drug when summarized by relationship.
- If a subject reports multiple preferred terms for a system organ class, the subject will be counted only once for that system organ class.
- Subject listings will be provided for any deaths, serious adverse events, and adverse events leading to withdrawal.

#### Sedation Assessment

- Sedated and alert scale as measured using a 100-mm linear VAS will be summarized by time point.
- Sleepy and Awake scale as measured using a 100-mm linear VAS will be summarized by time point.

